11.1 Compliance with ethical standards

All researchers in this research will conduct this research following the Declaration of Helsinki (revised in 2013) and the Ethical Guidelines for Medical Research Involving Human Subjects (Ministry of Education, Culture, Sports, Science, and Technology and Ministry of Health, Labor and Welfare, enforced in 2015).

The principal investigator should obtain and store the consent explanatory documents and opt-out documents approved by the assigned research organization.

11.2 Revision of the Implementation Plan

If the principal investigator determines that the protocol must be revised, he, or she will do so. If it is determined necessary to revise the consent explanatory document due to a change in the content of the protocol, the principal investigator will promptly revise it and obtain renewed consent from patients who gave consent before the revision, whether they wish to continue participating in the research or not. If it is deemed necessary to revise the consent document due to changes in the content, the document will be revised promptly, and the patients who gave consent before the revision will be asked whether they wish to continue participating in the research or not.

11.3 Reporting to the Head of the Research Organization

The principal investigator must submit a written report to the director of the research institution every year following the start of the study, except times when the research protocol is revised or when a serious adverse event occurs, when this study is discontinued or when there is a serious deviation from the protocol.

11.4 Protection of Personal Information

Handle patients' data (samples, medical information, etc.) with care and ensure the protection of their privacy.

In data reporting, a code for patient identification (personal identification code) is used and

no personal information is required (anonymization). Each anonymized information in the Department of Cardiovascular, Nephrology, and Neurology, Graduate School of Medicine, University of the Ryukyus will be managed by the information manager ([name]) on a dedicated computer that is not linked to the Internet. Additionally, each facility will keep a list of the correspondence between personal identification codes and personal information. The list of correspondence between personal identification codes and personal information will not be presented to the secretariat or [name], the person in charge of analysis. Verify the method of obtaining IC at each facility, as well as if appropriate procedures are being followed by those providing samples and information. The principal investigator and the person in charge at the collaborating institution must fully control the patient study-related samples and not take them out of the hospital. Furthermore, the samples will be stored until five years after the completion of the research or three years after the publication of the results, whichever is later.

11.5 Health Damage Compensation

Since benz bromarone and febuxostat are already covered by insurance, no compensation will be given for health problems, and health problems will be treated using normal health insurance.

What to do in the event of a health hazard

Emergency relief for patients does not depend on the presence or absence of negligence, the percentage of negligence, or the causal link with the target drug.

The priority will be given to implementation.

Despite the proper use of the target drugs specified in this study following the instructions of the physician in charge

For health damage brought on by side effects that occur, the use of the drug is within the scope of the indication, so the drug is subject to adverse drug reactions.

The Harm Reduction Program applies to it.

11.6 Secondary Use of Information

The potential for secondary use of the data collected for this study for other studies, etc., should be discussed in the explanatory document, and the subject's written consent should be obtained. Before using the data from this study is to be used for unrelated purposes, the study plan must receive the Ethical Review Committee's approval. Subjects who previously gave their consent for this protocol (Version 5.0) will be re-consented for secondary use.

12. Handling of samples and information

The E RED Cap of the Center for Clinical Research Education and Management at the University of the Ryukyus will serve as the study's EDC system. Essential documents related to this study (e.g., copy of application form, notification letter from the hospital director, consent form, case report form, patient identification code, and other documents or records necessary to ensure the accuracy of the data) will be kept in the Department of Cardiovascular, Nephrology, and Neurology, Graduate School of Medicine, University of the Ryukyus, will retain key study records for 5 years following the study' conclusion. Data from patients who withdraw their consent will be destroyed immediately. Blood samples collected and stored for this study will be discarded after the necessary marker measurements are completed.

13. Cost burden for subjects

The cost of measuring the inflammatory markers and oxidative stress needed for this study will be covered by research funds. All additional medications, observations, and tests necessary for this study will be covered by insurance. Therefore, there will be no additional burden on subjects due to participation in the study.

Subjects who partook in the study will be rewarded for their cooperation with rice vouchers worth 3,000 yen at three points: just before the start of the study, at 8 weeks, and 52 weeks.

14. Quality control and reliability assurance

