4.7 Completion, discontinuation, and suspension of study

(1) Criteria for completion of study

Subjects will be discontinued from the study if any of the following occur

a) Ineligibility as a subject

- (1) If it is discovered after the study has begun that the subject was ineligible for inclusion and exclusion requirements, etc.
- (2) If it is discovered after the research has begun, the patient's circumstances or other factors make it impossible to continue conducting the required observations (examinations).
- (3) If it comes to light that you are pregnant or think you might be.

If the uric acid level falls to less than 3 mg/dl following the start of administration

b) The subject's offer (withdrawal of consent)

If a subject case requests to discontinue participation in the study after it has begun

c) Transfer to another hospital

If the study's subject case is moved to a different hospital after it begins

d) clinical development

- (1) If the subject passes away following the start of the research
- (ii) If, following the start of the research, the subject becomes unable to follow the protocol due to cardiovascular complications (onset or worsening of heart failure, acute myocardial infarction, cerebrovascular accident, new onset of peripheral arterial disease, or the introduction of renal replacement therapy).

e) Discontinuation due to the onset of adverse events

If adverse events, etc. make it impossible to follow the implementation plan

f) Other

When the in-charge doctor determines that the research should be stopped.

(2) Procedure for discontinuing the research

If the subject is determined to fall under the discontinuation criteria, the physician in charge will explain this and stop the research.

If a safety issue, such as the occurrence of an adverse event, requires the study to be terminated, the responsible physician will take prompt appropriate measures and, in theory, will continue to monitor the patient until recovery or until it is decided that additional investigation is not required.

If it is discovered after the study has begun that the subject is unable to travel to the hospital due to circumstances, etc., the subject's health will be confirmed by telephone, etc., along with the reason for the absence and safety of the subject will be confirmed.

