The physician in charge of cases where the research has been stopped should detail the date of discontinuation, the reason for discontinuation, the processing, observations up to Visit 3 (week 8), and Visit 4 (week 52), even after discontinuation for potential cases, test results that can be gathered, and subsequent progress in the case report form.

5. survey items and schedule

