9.3 Withdrawal of Consent

Even if a subject consents to participate in the study, he, or she has the right to leave at any time, for any reason. In such a situation, the physician in charge of the subject will give the best medical care attainable so that the subject will not suffer any kind of disadvantage.

10. Benefits and disadvantages of subjects

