5.2. Participant flow

Number of registered participants, randomized participants, analysis population, treatment discontinuation and drop-out will be summarized in Figure (Participant flow) .

Participants who did not receive randomized treatment, those who were excluded after registration, those who discontinued treatment or dropped out will be summarized by reason. Drop-out rate will be estimated as number of participants with discontinuation and drop-out / number of FAS. These results will be included in Figure (Participant flow) .

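### Immediate destruction of data on consent withdrawal, which section 4.7 equates with any request to leave the study, conflicts with the recording rule for stopped cases and with the ITT and adverse event analyses

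*Protocol*

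**What the plan says.** Protocol section 12 (Handling of samples and information) contains one sentence on the point: "Data from patients who withdraw their consent will be destroyed immediately". It is not limited to samples, identifiers or future data, and does not depend on the patient asking for deletion. The same section has key study records, among them case report forms, kept for five years.

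Section 4.7(1) b) sets the trigger. Its heading glosses the subject's own request as withdrawal of consent, and the condition reads "If a subject case requests to discontinue participation in the study after it has begun". Section 9.3 adds that "she has the right to leave at any time, for any reason".

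Two other stopping routes in 4.7(1) are separate. Item e) reads "If adverse events, etc. make it impossible to follow the implementation plan" and item f) "When the in-charge doctor determines that the research should be stopped".

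Section 4.7(2) tells the physician what to enter for stopped cases: date, reason, observations to Weeks 8 and 52 "even after discontinuation for potential cases, test results that can be gathered, and subsequent progress in the case report form". It does not exempt item b).

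Section 7.2 calls for ITT analysis and for the frequency of each adverse event. In the statistical analysis plan in the same file, section 5.2 says that "those who discontinued treatment or dropped out will be summarized by reason". Section 3 of that plan leaves out of the full analysis set, and of the safety set, patients without information after randomisation.

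**The concern.** A site that follows section 12 erases the study record of a randomised, treated patient who asks to leave. A site that follows section 4.7(2) completes that record. Both cannot be done, and the choice decides whether the patient contributes to the ITT and adverse event comparisons.

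The loss could be selective. The physician is told the allocation (section 4.3), no blinding is described, the dosing schedules differ (section 4.4), and the listed adverse reactions differ between the drugs (section 6.2). Requests to leave may therefore differ by arm and be related to outcome.

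The loss is also hard to see afterwards. Ordinary drop-out leaves baseline and partial follow-up data for a sensitivity analysis. Destruction leaves none, and it puts the patient in exactly the state that the analysis sets exclude.

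**Working it through.** **1. The planned size, to see whether power is at issue.** Inputs from protocol section 4.2: difference 15, SD 20 mL/min/1.73m², two-sided 5%, power 90%, drop-out 20%.
- Normal approximation: n = 2(1.96 + 1.2816)² × (20/15)² = 37.4, so 38 per arm; 38/0.8 = 47.5, so 48 per arm, 96 in total.
- t-test: 38.35, so 39 per arm; 39/0.8 = 48.75, so 49 per arm, 98 in total, against the stated 100.
- With 40 per arm left after 20% loss, power is 0.918 (normal) or 0.912 (t-test).

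The stated size reproduces to within two patients, and 20% loss is already allowed for. The issue is possible bias, not power.

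**2. The rules side by side.**
- Item b), the patient asks to leave: section 12 destroys; section 4.7(2) records. Conflict.
- Items e) and f), adverse event or physician decision: section 12 does not apply; section 4.7(2) records. No conflict.
- A patient with an adverse event who asks to leave fits both b) and e). No rule says which takes precedence, so the data may meet either fate.

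**3. Effect on the analysis sets.** A treated patient with eGFR at Visits 2 and 3 meets the full analysis set definition in section 7.2. After destruction the same patient no longer does.

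The bookkeeping can also move. As an illustration, take the planned 20% drop-out as 20 of 100, and assume that 5 of the 20 are erased and leave both numerator and denominator. The drop-out rate of analysis plan section 5.2 becomes 15/95 = 15.8% instead of 20/100 = 20%. Similarly, section 5.4 of that plan triggers multiple imputation when at least 5% of participants lack the primary outcome. If only 5 of 100 lack it, that is 5.0% and the trigger is met. If those 5 are the erased patients and are no longer counted, it is 0/95 = 0% and the trigger is missed.

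**4. Possible size for adverse events.** The documents give no number of withdrawals, so the following is assumption. In an arm of 50 with k true cases, let w of those cases ask to leave and be erased. The observed rate is (k − w)/(50 − w).
- k = 10 (20%): w = 1 gives 9/49 = 18.4%; w = 3 gives 7/47 = 14.9%; w = 5 gives 5/45 = 11.1%.
- k = 5 (10%): w = 1 gives 4/49 = 8.2%; w = 3 gives 2/47 = 4.3%; w = 5 gives 0/45 = 0%.

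**5. Possible size for eGFR change.** If the w erased patients have a mean change d worse than the rest, the arm mean shifts by w × d/50. For d from 3 to 10 mL/min/1.73m²:
- w = 1: 0.06 to 0.2
- w = 3: 0.18 to 0.6
- w = 5: 0.3 to 1.0

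At Week 52 this applies only to patients whose Visit 4 value would otherwise exist, because they would have agreed to follow-up or withdrew after Visit 4.

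**The case against.** A reader might infer that the data of everyone who quits because of the drug disappear. The documents do not support that. Item b) concerns leaving the study, not stopping the drug. Stops for adverse events or by the physician have their own items, which section 12 does not reach. Follow-up until recovery in section 4.7(2) applies where a safety issue requires termination, so it is not contradicted.

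A reader might also infer that no trace of an adverse event would remain. Section 8 has events entered in the medical file as well as the case report form, and serious ones reported to the head of the institution. Section 12 does not say that its rule covers those records or the allocation table. They may survive, although the text does not say so.

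A third inference would be that the primary comparison is beyond repair. The primary endpoint is Visit 4 minus Visit 2. A patient who leaves earlier and refuses follow-up lacks it with or without destruction, and keeping earlier data does not recover it. If withdrawals are counted by arm, the missing outcomes can be bounded.

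It can fairly be added that section 4.7(2) asks only for what can be gathered, so the clash with section 12 is a missing exception. The analysis sets shrink under destruction, but their definitions are not contradicted. The consent pages are not available and may define what withdrawal covers.

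These points narrow the concern without removing it. Section 12 still has no exception for data in hand, section 4.7(2) has none for item b), and the patient who fits both b) and e) has no assigned rule.

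**Conclusion.** The point holds for patients who leave at their own request. For them the protocol orders both recording and destruction, and destruction is incompatible with a full ITT analysis and a complete adverse event count. The exposed data are adverse events in the study database and the baseline and Week 8 values that feed the secondary outcomes, the GEE analysis and multiple imputation. Week 52 values are exposed only where the patient would have agreed to follow-up or withdrew after Visit 4.

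The size cannot be derived from the documents. The ranges above rest on assumed numbers of erased patients, all in one arm and, for the event rates, all with an event. They show that a few records can matter for event rates in arms of 50; they do not predict what will happen. The link between leaving and outcome is plausible in a trial without described blinding but is not shown. This should be fixed, and before the first withdrawal, because destruction cannot be undone.

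**What to change.** Reconcile sections 4.7(1), 4.7(2), 7.2, 8 and 12.
- In section 12, state that data collected up to withdrawal are retained and used in the full analysis and safety sets. Delete them only when the patient specifically asks, subject to the consent text and ethics committee approval. Say whether the rule reaches medical-file entries and serious event reports.
- In the participant flow, count deletions by arm.
- In 4.7, record three different decisions separately: stopping study drug while Visit 3 and 4 data continue, stopping follow-up, and refusing use of data. State how a case that fits both b) and e) is classified for data handling.

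This changes data handling only; the clinical stopping criteria are left as they are. The cost is an ethics amendment and matching consent wording. Where the patient refuses both follow-up and data use, the loss remains, but it is counted.

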14.1 Monitoring

Monitoring will be performed to ensure that the study is being conducted safely and based on the protocol and that data are being collected appropriately.

Monitoring officer: [name], Director, Center for Clinical Research Education and Management

The monitoring items shall be as follows, and the implementation of on-site monitoring shall be deemed necessary.

- 1) Process for obtaining consent and storage of consent forms
- 2) Eligibility
- 3) Observed item data
- 4) Adverse events (especially serious adverse events and their reporting status)
- 5) Protocol treatment status
- 6) Other

14.2 Auditing

An audit will be conducted to ensure the reliability of this research.

Audit Manager: [name], Deputy Director, Clinical Research Support Center

The audit will focus on the following items

- 1) Status of compliance with ethical guidelines and research protocol
- 2) Process for obtaining consent and storage of consent forms
- 3) Ethical Review Status
- 4) Occurrence and review status of serious adverse events
- 5) Accuracy of collected data items
- 6) Other

14.3 Research Support

The University of the Ryukyus will dispatch research assistants when requested by other institutions.

15. Research funding sources and conflicts of interest

The funds for this study will be contributed by Teijin Pharma Limited based on a joint research agreement with the Third Department of Internal Medicine. Teijin Pharma Limited will not partake in any way in the management of this study, including planning, execution, analysis, and publication. Participants in this study are required to abide by the conflict of interest management guidelines and shall not break them.

16. Disclosure of information on research and publication of research results

16.1 Clinical Research Registration

This study has been registered in the University Hospital Medical Information Network Clinical Trials Registration System ((identification number: R000029056)) before the start of the study and the information has been made public.

16.2 Research presentation

After the completion of the research, the principal investigator will promptly summarize the results and publish them by presenting them at a conference or submitting a paper.

17. Research organization

The objective of this Statistical Analysis Plan (SAP) is to define detailed method for data management and statistical analysis for “Urate lowering drugs Randomized parallel-group Comparison study in the Chronic Kidney Disease patients with hypertension and hyperuricemia (URIC-CKD study)”.

2. Study design

Summary of research is shown below.

2-1. Study objective

To evaluate the effect of uric acid production inhibitors (xanthine oxidase inhibitors) and uric acid excretion enhancers (uric acid transporter URAT 1 inhibitors) on renal function decline in patients with chronic kidney disease (CKD) complicated by hyperuricemia and hypertension.

2-2. Target population

2-2-1. Inclusion criteria

Patients must meet all of the following criteria (1) through (7) at the time of eligibility determination.

- (1) Patients with a serum uric acid level greater than 7.0 mg/dL
- (2) Patients with hypertension (untreated patients with an office blood pressure of 140/90 mmHg or higher or on antihypertensive medication) who have not changed their antihypertensive medication for 8 weeks prior to the eligibility determination
- (3) Patients with CKD stage 3a-3b
- (4) Age 20 years or older at the time of obtaining consent
- (5) Outpatients
- (6) Patients with no history of gout
- (7) Patients who have given their written consent to participate in the study.

2-2-2. Exclusion criteria

If any of the following items (1) through (13) are violated at the time of eligibility determination, the company shall be excluded from the scope.

- (1) Patients with a history of hypersensitivity to the drugs used
- (2) Patients whose AST or ALT is more than twice the institutional standard value
- (3) Patients with severe renal dysfunction (eGFR less than 30 mL/min./1.73m² or more than 60 mL/min./1.73m², dialysis patients)
- (4) Patients taking thiazide diuretics, loop diuretics
- (5) Patients who have received uric acid lowering drugs in the 2 weeks prior to eligibility determination

- (6) Patients who developed coronary artery disease within 3 months prior to eligibility determination
- (7) Patients with concomitant or prior malignancies (unless the malignancy has been untreated for at least 5 years since the time of eligibility determination and is judged not to have recurred)
- (8) Patients receiving any of the following drugs: mercaptopurine hydrate, azathioprine, pyrazinamide, ethambutol
- (9) Patients taking warfarin
- (10) Patients who are lactating, pregnant, or may be pregnant
- (11) Patients who have participated in other clinical studies (including clinical trials) within 6 months prior to eligibility determination
- (12) Patients with urinary tract stones
- (13) Other patients whom the physician in charge judges to be unsuitable as subjects.
- (14) Patients with serum uric acid levels below 7.0 mg/dl in the post-visit 2 lifestyle guidance phase will not be randomized to the treatment phase. (Final eligibility check)
- (15) Patients with a history of acute myocardial infarction, acute coronary syndrome, intervention for coronary artery stenosis (catheterization and coronary artery bypass surgery), ventricular tachycardia, multisource ventricular arrhythmia, or acute heart failure within 3 months prior to the time of eligibility determination (newly added based on the results of the CARES study)

2-3. Study design

A multi-center, randomized, parallel-group comparison trial

2-4. Random allocation

Participants will be randomly allocated to:

Treatment group A (lifestyle guidance + benzbromarone) or

Treatment group B (lifestyle guidance + febuxostat)

2-5. Research treatment

URAT 1 inhibitor: benzbromarone (Urinorm® tablet)

Xanthine oxidase inhibitor: febuxostat (Feburic® Tablets)

2-5-1. Run in period

During the Run in phase (8 weeks), lifestyle guidance (diet, restriction of alcohol consumption, exercise recommendations, etc.) will be given with reference to the Guidelines for the Treatment of Hyperuricemia and Gout (2nd edition).

2-5-1. Treatment period 1

After final eligibility determination, febuxostat 10 mg/day or benzbromarone 25 mg/day will be administered in treatment phase 1 after confirming tolerability in addition to lifestyle guidance. The dose of febuxostat will be increased to 20 mg/day from week 5. The duration of treatment should be 8 weeks.

2-5-2. Treatment period 2

The medication used in treatment phase 1 should be adjusted to achieve a serum uric acid level of less than 6 mg/dl. The treatment period should be 44 weeks (1 year from the start of the drug).

2-6. Endpoint

2-6-1. Primary endpoint for efficacy

Change in eGFR from immediately before initiation of randomized treatment (visit2) to 52 weeks after initiation of treatment (visit 4):

(eGFR at visit 4 – eGFR at visit2) / eGFR at visit 2 [unit: % / 52 weeks] and
eGFR at visit 4 – eGFR at visit 2 [unit: ml / min / 1.73m² / 52 weeks]

2-6-2. Secondary endpoint for efficacy

- (1) Change in eGFR from immediately before initiation of randomized treatment (visit2) to 8 weeks after initiation of treatment (visit 3) [unit: % / 52 weeks and ml / min / 1.73m² / 8 weeks]
- (2) Change in office blood pressure from immediately before initiation of randomized treatment (visit2) to 8 & 52 weeks after initiation of treatment (visits 3 & 4) [unit: % / 8 weeks, % / 52 weeks, mmHg / 8 weeks and mmHg / 52 weeks]
- (3) Difference in change in eGFR from immediately before initiation of randomized treatment (visit2) to 8 weeks after initiation of treatment (visit 3) (per 4 weeks) and change in eGFR from 8 weeks to 52 weeks after initiation of treatment (visit 4) (per 4 weeks) [unit: % / 4 weeks and ml /min / 1.73m² / 4 weeks]

Difference in change in eGFR from immediately before initiation of randomized treatment (visit2) to 52 weeks after initiation of treatment (visit 4) (per 4 weeks) and change in eGFR from initiation of run-in period (visit 1) to initiation of randomized treatment (visit 2) (per 4 weeks) [unit: % / 4 weeks and ml /min / 1.73m² / 4 weeks]

Difference in change in eGFR from 8 weeks (visit 3) to 52 weeks after initiation of treatment (visit 4) (per 4 weeks) and change in eGFR from initiation of run-in period (visit 1) to initiation of randomized treatment (visit 2) (per 4 weeks) [unit: % / 4 weeks and ml /min / 1.73m² / 4 weeks]

- (4) Change in serum uric acid level from immediately before initiation of randomized treatment (visit2) to 8 & 52 weeks after initiation of treatment (visits 3 & 4) [unit: % / 8 weeks, % / 52

weeks, mg / dl / 8 weeks and mg / dl / 52 weeks]

Rate of attainment of serum uric acid level <6.0 mg/dl at 8 & 52 weeks after initiation of treatment (visits 3 & 4) [unit: %]

(5) Change in urinary albumin / creatinine ratio from immediately before initiation of randomized treatment (visit2) to 8 & 52 weeks after initiation of treatment (visits 3 & 4) [unit: % / 8 weeks, % / 52 weeks, mg / gCr / 8 weeks and mg / gCr / 52 weeks]

(6) Change in urine pH from immediately before initiation of randomized treatment (visit2) to 8 & 52 weeks after initiation of treatment (visits 3 & 4) [unit: % / 8 weeks, % / 52 weeks, absolute change / 8 weeks and absolute change / 52 weeks]

(7) Change in XO activity from immediately before initiation of randomized treatment (visit2) to 8 & 52 weeks after initiation of treatment (visits 3 & 4) [unit: % / 8 weeks, % / 52 weeks, pmol IXP / min / mL / 8 weeks and pmol IXP / min / mL / 52 weeks]

(8) Change in hs-CRP from immediately before initiation of randomized treatment (visit2) to 8 & 52 weeks after initiation of treatment (visits 3 & 4) [unit: % / 8 weeks, % / 52 weeks, mg / dL / 8 weeks and mg / dL / 52 weeks]

(9) Change in urinary 8-OHdG (8-hydroxy-2'-deoxyguanosine) from immediately before initiation of randomized treatment (visit2) to 8 & 52 weeks after initiation of treatment (visits 3 & 4) [unit: % / 8 weeks, % / 52 weeks, ng / mL / 8 weeks and ng / mL / 52 weeks]

(10) Change in urinary angiotensinogen from immediately before initiation of randomized treatment (visit2) to 8 & 52 weeks after initiation of treatment (visits 3 & 4) [unit: % / 8 weeks, % / 52 weeks, μ g / gCr / 8 weeks and μ g / gCr / 52 weeks]

(11) Change in urinary L-FABP from immediately before initiation of randomized treatment (visit2) to 8 & 52 weeks after initiation of treatment (visits 3 & 4) [unit: % / 8 weeks, % / 52 weeks, μ g / gCr / 8 weeks and μ g / gCr / 52 weeks]

2-7. Sample size estimation

Expected number of participants: 100 (50 in each of treatment groups A and B)

[Rationale for sample size estimation]

The main objective of this study was to exploratively investigate the effect of febuxostat administration and benz bromarone on renal function in patients with hyperuricemia complicated by chronic kidney disease. Based on the results of previous studies, we expected the difference between the two treatments to be eGFR/52W 15 ml/min/1.73m².^{1,2} Then, we calculated α 0.05, power 0.8, δ 15, σ 20, and dropout rate as 20%.

2-8. Follow-up duration

Participants will be followed up for 52 weeks (treatment period 1 for 8 weeks and treatment period 2 for 44 weeks).

2-9. Research period

Research period: from approval by the Ethical Review Committee to February 28, 2021

Registration period : from approval by the Ethical Review Committee to November 30, 2018

3. Analysis population

Full analysis set (FAS): In accordance with the intention to treat (ITT) principle, all patients except for those without information after randomization will be included in the analysis.

Per protocol set (PPS): Sensitivity analysis excluding participants with protocol violation might be conducted.

Safety analysis set (SAS): All patients except for those without any information after randomization who received any randomized treatment will be included in safety analysis.

4. Data management

